#### **6.6.7 Disease progression/worsening of systemic lupus erythematosus**

Disease progression can be considered as a worsening of a subject's condition attributable to SLE. It may be an increase in the activity or severity of the existing manifestations of SLE or the appearance of new manifestations. Worsening of SLE should not be reported as an AE, unless the signs and symptoms meet criteria for an SAE.

## 6.7 Reporting of serious adverse events

All SAEs have to be reported, whether or not considered causally related to the investigational product, or to the study procedure(s). All SAEs will be recorded on the CRF. PRA Safety Management is to be sent all safety forms and supporting documentation including laboratory tests, imaging reports, diagnostic test results, biopsy reports, and discharge summaries.

If any SAE occurs in the course of the study, then Investigators or other site personnel are to inform PRA Safety Management within 1 day, ie, immediately but **no later than 24 hours** after he or she becomes aware of it.

PRA Safety Management works with the Investigator to ensure that all the necessary information is provided to the PRA safety data entry site **within 1 calendar day** of initial receipt for fatal and life-threatening events (if received for instance during a weekend or a public holiday, the information is forwarded as early as possible on the first business day following the weekend or holiday) and **within 3 calendar days** after initial receipt for all other SAEs.

For fatal or life-threatening AEs where important or relevant information is missing, active follow-up is undertaken immediately. Investigators or other site personnel inform PRA Safety Management of any follow-up information on a previously reported SAE within 1 calendar day, ie, immediately but **no later than 24 hours** after he or she becomes aware of it.

Once the Investigators or other site personnel indicate an AE is serious or is an AESI in the Datalabs system, an automated email alert is sent to the designated PRA and AstraZeneca representative(s).

If the Datalabs system is not available, then the Investigator or other study site personnel reports a SAE to PRA Safety Management on the study-specific paper SAE form by telephone, fax, or email. The SAE report form must be completed in the electronic system as soon as the system is available again.

## 6.8 Reporting of adverse events of special interest

Adverse events of special interest will be assessed by the Investigator for severity, relationship to the investigational product, possible aetiologies, and whether the event also meets criteria of an SAE. All AESIs (serious or nonserious) will be recorded on the AE CRF (using a recognised medical term or diagnosis that accurately reflects the event).

The reporting period for AESIs is the period immediately following randomisation through the end of subject participation in the study. Adverse events of special interest that occur prior to randomisation in the LTE study should be reported in Studies D3461C0004 or D3461C00005. Following detection of an AESI (nonserious), reporting is required within 72 hours of knowledge of the event, and for serious AESIs the standard 24-hour timeline for reporting to the appropriate AstraZeneca representative or designee applies. Nonserious non-opportunistic infections will not be captured as AESIs.

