### **6.5 Adverse events of special interest**

An AESI is an AE of scientific and medical concern specific to understanding biologics and requires close monitoring and rapid communication by the Investigator to the Sponsor/Sponsor's delegate. An AESI may be serious or nonserious.

Adverse events of special interest in this protocol will be assessed at each visit on the CRF. The events of interest are medically significant infections (non-opportunistic serious infections and opportunistic infections including viral infection/reactivation), severe hypersensitivity reactions including anaphylaxis and immune complex disease, malignancy, *herpes zoster* with cutaneous presentation, TB (including latent TB), influenza, vasculitis (non SLE), and MACE (including stroke, myocardial infarction, or cardiovascular death). Lupus nephritis (associated with SLE; WHO or ISN/RPS Classification Class III, IV or V) is defined

not as an AESI but as a new SLEDAI AE, and diagnosis will be supported with laboratory results.

An AESI that meets 1 of the seriousness outcomes listed in Section 6.2 will be categorised as an SAE for the purposes of follow-up responsibility and safety reporting. A nonserious AESI will be categorised as an AE. For reporting of AESIs, see Section 6.8.

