#### **6.5.1.3 Influenza**

Influenza is a severe viral infection that includes the following symptoms: temperature greater than 100.8°F (38.2°C), and malaise, headache, or myalgia. It is often accompanied by nausea, vomiting, and diarrhoea, and at least 1 of the following respiratory symptoms: cough, sore throat, or shortness of breath.

Laboratory criteria for influenza include at least 1 of the following: isolation of influenza virus from a clinical specimen, detection of influenza virus nucleic acid in a clinical specimen,

identification of influenza virus antigen by direct fluorescent antibody test in a clinical specimen, OR influenza-specific antibody response.

A confirmed case of influenza meets the clinical and laboratory criteria for the viral illness. Laboratory confirmation should be done using locally available, rapid, commercial tests approved by regulatory agencies and sampling respiratory specimens. Not all upper respiratory viral infections or gastrointestinal viral infections are influenza. In the case where a subject reports a viral infection severe enough to be considered, in the opinion of the Investigator, influenza, a viral test should be performed (if possible) to confirm the diagnosis. If, in the opinion of the Investigator, the subject has had influenza (the specific viral infection), this should be reported as an AESI, whether or not a test to confirm the diagnosis has been performed. Less severe viral infection should be reported as an AE only.

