#### **6.5.4 Herpes zoster reactivations (including cutaneous events)**

*Herpes zoster* is a viral infection characterised by a cutaneous vesicular eruption on an erythematous base presenting along dermatome(s) and usually associated with prodromal pain. *Herpes zoster* results from the reactivation of *varicella zoster* virus; multiple dermatomes may be involved (>3 indicates disseminated disease) and organ or systemic infection may occur (invasive; therefore an opportunistic infection). Polymerase chain reaction testing of samples from vesicles, biopsy, or other specimens (eg, cerebrospinal fluid) may confirm the presence of *varicella zoster* virus. Herpes Zoster reactivation with cutaneous presentation is an identified risk.

. Systemic infections or other medically significant herpes zoster infections are considered important potential risks and classified as *medically significant infections* for adverse event reporting in this study unexpected for regulatory reporting purposes. For additional information regarding *herpes zoster*, refer to the IB. As all herpes zoster events are considered to be an AESI, the Sponsor will collect information including whether or not

subjects have received vaccination for *herpes zoster*. The *herpes zoster* vaccine medical history data will be captured in the appropriate sections of the CRF.

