If an AE has a missing onset date, then unless the stop date of the AE indicates otherwise, it will be considered an AE in the categories above. Similarly, if an AE has a partial onset date, then unless the partial onset date or the stop date indicates otherwise, it will be considered an AE in the categories above. If the missing or partial start date does not allow an assignment of the event as during the Phase 3 feeder studies or the LTE study, the AE will be assigned to the study in which it was documented.

Adverse events of special interest are marked as such in the electronic Case Report Form (eCRF).

Major acute cardiovascular events (MACEs) will be determined according to the assessments of the Cardiovascular Event Adjudication Committee (CV-EAC).

An infusion-related reaction (as assessed by the investigator) is defined as an AE with a preferred term of “Infusion related reaction”.

An infection is defined as an AE within the MedDRA system organ class infections and infestations.

Opportunistic infections are those marked in the eCRF as assessed by the investigator as opportunistic and non-opportunistic infections are all infections not marked as opportunistic by the investigator.

Hypersensitivity is defined as adverse events with MedDRA preferred term (PT) = “Hypersensitivity” and Lower level term (LLT) = “Hypersensitivity reaction”.

Herpes zoster is further classified according to the information given on the Herpes zoster log as follows:

Category	Rash [Y/N]	Episode status of HZ Event [localized/ disseminated]	Specify Disseminated [cutaneous/ systemic]	Any organ involvement [Y/N]
Cutaneous (localised) herpes zoster	Y	Localized	[no rule]	N
Cutaneous disseminated herpes zoster	Y	Disseminated	Cutaneous	[no rule]
Visceral disseminated herpes zoster	[no rule]	Disseminated	Systemic	[no rule]

A COVID-19 related adverse event is defined as an AE with one of the following preferred terms: “Asymptomatic COVID-19”, “Congenital COVID-19”, “Coronavirus infection”, “Coronavirus pneumonia”, “Coronavirus test positive”, “COVID-19”, “COVID-19 pneumonia”, “Post-acute COVID-19 syndrome”, “SARS-CoV-2 antibody test positive”, “SARS-CoV-2 carrier”, “SARS-CoV-2 sepsis”, “SARS-CoV-2 test false negative”, “SARS-CoV-2 test positive”, “SARS-CoV-2 viraemia”, “Suspected COVID-19”, “Vaccine derived SARS-CoV-2 infection”.

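### The sentence excluding nonserious non-opportunistic infections from AESI capture (Protocol 6.5.1.1 and 6.8) is unscoped and, read literally, contradicts the rules that make herpes zoster, influenza and latent TB AESIs

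*Protocol*

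**What the plan says.** The primary outcome is the rates of AESIs and SAEs (Protocol 2.1, SAP 1.1.1). On which infections are AESIs, the protocol says:

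- **6.5**: "An AESI may be serious or nonserious". Its list names cutaneous herpes zoster separately from medically significant infections, and then "TB (including latent TB), influenza, vasculitis (non SLE), and MACE".
- **6.5.1.1**, closing the definition of serious non-opportunistic infection: "Nonserious non-opportunistic infections will not be captured as AESIs".
- **6.5.1.3**: if the investigator judges that the subject had influenza, "this should be reported as an AESI, whether or not a test to confirm the diagnosis has been performed". There is no seriousness condition.
- **6.5.4**: "As all herpes zoster events are considered to be an AESI"; and "Herpes Zoster reactivation with cutaneous presentation is an identified risk".
- **5.2.7.1 and 5.2.7.2**: a newly positive QFT-G result is to be reported as an AESI. Inclusion criterion 8(b) says the same where the retest at entry is positive.
- **6.8**: "All AESIs (serious or nonserious) will be recorded on the AE CRF", with 72 hours allowed for reporting a nonserious one. The section then ends by repeating the 6.5.1.1 sentence word for word.

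SAP 3.1.1 states: "Adverse events of special interest are marked as such in the electronic Case Report Form". It defines non-opportunistic infections as all infections the investigator did not mark as opportunistic, with no carve-out. SAP 4.2.1.1 reports zoster, tuberculosis and influenza as AESI categories separate from non-opportunistic serious infections.

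**The concern.** Under 6.5.1.2 an opportunistic infection must be invasive, and under 6.5.4 zoster becomes opportunistic only with organ or systemic involvement. Localised cutaneous zoster is therefore non-opportunistic. When it is also nonserious, the closing sentence of 6.8 excludes it from AESI capture while 6.5.4 includes it. Ordinary influenza and latent TB are in the same position.

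A site that applied the sentence as written would record such an event as an AE but leave the AESI mark off. The event would then be missing from the AESI rates and the AESI Kaplan-Meier plots. The consequence is also operational: the mark triggers the automated alert (6.7), and AESI status sets the 72-hour timeline (6.8) and the request for cultures (6.9.2). Cutaneous zoster is where this matters most, since Protocol 1.3 reports a dose-related increase and calls it an identified risk. Equal under-marking in all arms would still shrink the absolute rates, which are what this study reports.

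**Working it through.** **1. The rules side by side**

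| Event, nonserious | Event-specific rule | 6.5.1.1 / 6.8 sentence read literally |
|---|---|---|
| Localised cutaneous zoster | AESI (6.5, 6.5.4) | Not an AESI |
| Influenza in the investigator's opinion | AESI (6.5, 6.5.1.3) | Not an AESI |
| Latent TB, newly positive QFT-G | AESI (6.5, 5.2.7) | Not an AESI |
| Any other non-opportunistic infection | None | Not an AESI (no conflict) |

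The conflict is confined to the first three rows. In 6.5.1.1 the sentence can be read as the boundary of one AESI class. In 6.8 it stands outside any class, so that scope is lost. For influenza the narrow reading is strained even within 6.5.1: the introduction there sorts infections into serious non-opportunistic or opportunistic, and nonserious influenza (6.5.1.3, same parent section) is neither.

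**2. Which follow-up time is exposed**

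AESIs before extension randomisation are reported in the feeder studies (6.8), whose protocols are not among the documents. Only extension time falls under this wording. The plan assumes 20% annual dropout on anifrolumab 300 mg, 30% on placebo, and 90% of completers entering (Protocol 8.2). I add one assumption, dropout at mid-year. Per subject randomised in a feeder study:

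- Anifrolumab 300 mg, feeder year: 0.90. Extension: 0.80 × 0.90 × 0.90 × (1 + 0.80 + 0.64) = 1.581. Total 2.481.
- Randomised Placebo, feeder year: 0.85. Extension, half re-randomised to placebo: 0.70 × 0.90 × 0.50 × 0.85 × (1 + 0.70 + 0.49) = 0.586. Total 1.436.

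Check against the plan's totals: 893 / 2.481 = 360 and 517 / 1.436 = 360. The same whole number of subjects in both groups indicates that the reconstruction is close to the plan's own. The extension share is 1.581 / 2.481 = 64% for Randomised Anifrolumab 300 mg (36% feeder) and 0.586 / 1.436 = 41% for Randomised Placebo.

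**3. Illustration only**

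Let f be the share of events in these categories that are nonserious and non-opportunistic, s the share of those left unmarked in the extension, and L the extension share of subject-years. With a constant rate, the recorded rate is true rate × (1 − f × s × L). The documents give neither f nor s. The starting value of 10 per 1000 subject-years is the plan's generic AESI illustration, not a zoster rate.

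| f | s | Anifrolumab 300 mg (L = 0.637) | Placebo (L = 0.408) |
|---|---|---|---|
| 0.25 | 0.10 | 9.8 | 9.9 |
| 0.50 | 0.50 | 8.4 | 9.0 |
| 0.75 | 0.50 | 7.6 | 8.5 |
| 0.95 | 1.00 | 3.9 | 6.1 |

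Applying the loss to all subject-years (L = 1) would give 9.75, 7.5, 6.25 and 0.5, which overstates it. With equal f and s the loss is larger in the anifrolumab group, because more of its time is extension time. For scale, SAP 4.1.3 gives an exact 95% CI of 4.56 to 19.03 at 10 per 1000 on 893 subject-years, which I reproduce. A shift to 7.6 lies well inside that interval, so the interval would not reveal it.

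**The case against.** The strongest reply is that no careful site would be misled. The sentence belongs to 6.5.1.1, where it closes one class, and 6.8 merely repeats that boundary. Zoster, influenza and TB are listed separately and have their own explicit instructions. A 72-hour rule for nonserious AESIs sits in the same section. The SAP keeps these events as separate categories and breaks zoster down by seriousness and by mild, moderate or severe intensity, which presupposes nonserious events. This stands as evidence of intent: inclusion is what the authors meant. It does not remove the literal conflict, because 6.8 carries no scope and the mark is made at the site.

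Two stronger inferences are tempting and are not supported:

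- A reader might infer that most events of the identified risk count or not according to which section a site follows. The sentence also stands inside 6.5, so this is not 6.8 against 6.5; several specific rules outweigh one general sentence; and the documents give no figure for the nonserious share.
- A reader might infer that unmarked zoster is lost to the analysis, including the first-onset zoster summary. SAP 4.2.1.1 does not tie that summary to the AESI mark. SAP 3.1.1 sub-classifies zoster from a dedicated log, and an unmarked event would still appear in the all-AE tables and, if coded to infections and infestations, in the infection summaries. Loss from that table is possible, not established.

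The eCRF and its completion guidance are not among the documents and may already settle the matter.

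**Conclusion.** The wording conflict is real and bears on a component of the primary outcome. It is a drafting inconsistency with a clear intended reading, not evidence that events were missed.

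If sites did under-mark, the effect would be downward, on the AESI summaries and AESI Kaplan-Meier estimates, and limited to extension time: about 64% of subject-years in the Randomised Anifrolumab 300 mg group and 41% in Randomised Placebo. Those shares rest on the plan's dropout and entry rates plus mid-year dropout. The size of any loss rests on f and s, for which the documents offer nothing; the illustrated range runs from negligible (9.8 per 1000 for a true 10) to 3.9 in the extreme case where every site applies the sentence and 95% of events are nonserious. No point in that range is an estimate. The change is worth making because it is nearly free and because the plan states no check that would show whether the problem arose.

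**What to change.** 1. **Protocol 6.5.1.1 and 6.8.** Limit the sentence to infections not otherwise listed as AESIs in 6.5, and state that herpes zoster, influenza and TB including latent TB remain AESIs whether serious or not. Put the same wording in the eCRF completion guidance.
2. **SAP 3.1.1.** Add a blinded reconciliation before database lock: compare zoster, influenza and TB preferred terms, and the Herpes zoster log, with the AESI mark, and query sites about unmarked events, to be judged by the 6.5 definitions. The blinded delivery reviews in SAP 2.2 are a natural place for it.

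Counting every matching preferred term automatically would be the wrong remedy. Under 6.5.1.3 less severe viral infection is an AE only, and under 6.5.5 latent TB needs a positive repeat test, so a term-based rule could add events that the protocol excludes.

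The current SAP (v5.0, April 2022) is later than the planned study end (Q3 2021). For data already collected, the reconciliation rather than the wording change does the work. The cost is one sentence in two sections, a note to sites, a preferred-term list and a small amount of query work. All AEs are already collected, so no new assessments are needed.

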## 6.9 Management of investigational product-related toxicities

### 6.9.1 Anaphylaxis, hypersensitivity, and infusion-related reactions

Infusion-related reactions have been reported with the administration of IV Ig and mAb. As with any antibody, allergic reactions to dose administration are possible. Therefore, appropriate drugs and medical equipment to treat acute anaphylactic reactions must be immediately available, and study personnel must be trained to recognise and treat anaphylaxis. For a definition of anaphylaxis, hypersensitivity reactions, and infusion-related reactions, [REDACTED]

Subjects should not be premedicated unless they have had a prior infusion-related reaction to anifrolumab. However, if a prior infusion-related reaction has been documented, the Investigator may elect to administer prophylactically an antihistamine and/or acetaminophen/paracetamol for the comfort and safety of the subject prior to subsequent infusions. Prophylactic use of glucocorticosteroids prior to subsequent infusions is not permitted.

### 6.9.2 Infections

When an infection is reported as an SAE or AESI, cultures should be obtained and culture results should be reported with the event. Other specific laboratory tests or other investigations (eg, chest x-ray for pneumonia) that confirm or aid in the diagnosis or treatment should be obtained when indicated, and results should be reported with the SAE or AESI. Failure to obtain this information will impair the Sponsor's ability to characterise the benefit:risk profile of anifrolumab.

Subjects who develop a new infection while undergoing treatment with investigational product should receive appropriate medical therapy, as determined by local standards, and be monitored closely until the condition resolves. Investigational product should not be administered to a subject with a clinically significant, active infection as determined by the Investigator (see Section 3.9). For any active infection (eg, *varicella zoster* infection/chickenpox) or significant exposure to any infection (eg, *varicella zoster* infection in

a naive subject, bacterial pneumonia), the Investigator should consider whether to interrupt investigational product administration and should notify the PRA Medical Monitor.

Similarly, if a subject presents with signs or symptoms where opportunistic infections are considered (eg, CNS symptoms consistent with progressive multifocal leukoencephalopathy or *herpes encephalitis* or atypical pneumonia suggesting *P jirovecii* pneumonia), investigational product should be interrupted until the Investigator confirms the symptoms and signs of infection have resolved or that no active infection has developed.

If dosing is resumed after resolution of a safety concern (ie, infection or other AE) the investigational product must be administered within 14 days after the scheduled time of the missed dose. If this is not possible, dosing should be resumed at the time of the next scheduled dose.

## **6.10 Study governance and oversight**

The safety of all AstraZeneca clinical studies is closely monitored on an ongoing basis by AstraZeneca representatives in consultation with PRA Safety Management. Issues identified will be addressed; for instance, this could involve amendments to the study protocol and letters to Investigators.

### **6.10.1 Data and Safety Monitoring Board**

An independent DSMB will perform evaluations of safety data at specified regular intervals throughout the study and make recommendations to the Sponsor regarding further conduct of the study. After reviewing the data, the DSMB may choose to unblind the treatment groups for additional review. The DSMB will not routinely review efficacy data.

At any time during the study, as well as on an *ad hoc* basis, the DSMB will also review any safety data assessed by the PRA Medical Monitor as medically relevant. Additional information, including frequency of DSMB review, can be found in the DSMB charter.

If any event(s) occur that, in the opinion of the DSMB, contraindicates further dosing of additional subjects, the Sponsor will conduct a prompt cumulative review of safety data and the circumstances of the event in question to determine whether dosing and study randomisation should be stopped, whether the protocol will be modified, or whether the study will be discontinued permanently. Review by the DSMB and Sponsor decision to resume (with or without modifications) is required for resumption of the study in the event the study is interrupted. Where applicable, the regulatory authorities and ECs will be notified of any actions taken with the study.

